We have developed human laboratory cocaine self-administration procedures that have strong predictive validity for determining the impact of behavioral manipulations on cocaine taking. For example, we have shown that the availability of mutually exclusive alternative reinforcers reduces cocaine self-administration. This arrangement models another effective psychosocial intervention, contingency management. In this pilot study, our self-administration procedures will be adapted to evaluate the influence of decisional analysis/craving regulation features of CBT on cocaine self-administration, thereby determining how these components contribute to the ability of CBT to promote biologically verified cocaine abstinence.

The specific aim of this project is to demonstrate that the decisional analysis/craving regulation aspects of CBT reduce cocaine self-administration in subjects with cocaine use disorder through diminished craving responses. Thirty non-treatment seeking human subjects meeting diagnostic criteria for cocaine use disorder will complete an outpatient, crossover, placebo-controlled study consisting of 1 practice and 9 experimental sessions. In each experimental session, the reinforcing effects of intranasal cocaine (0, 40 or 80 mg) will be determined under one of three regulation of craving conditions that simulate CBT decisional analysis (i.e., negative instruction, positive instruction or a neutral “look” condition). After sampling the dose of cocaine available in each session, subjects will complete the craving manipulation assigned to that session, they will then rate their craving and finally they will have the opportunity to earn the sampled dose in a progressive-ratio procedure. We hypothesize that focusing on the negative effects of cocaine use will decrease craving and reduce cocaine self-administration relative to the positive and “look” conditions, and that craving will be positively correlated with self-administration outcomes.

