2. OBJECTIVES

The primary objective of this study is to determine the influence of a craving manipulation on the reinforcing effects of cocaine.

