During the actual manipulation in experimental sessions, subjects will be presented 30 trials depicting cocaine images. Each trial will begin with an instruction presentation (i.e., positive, negative, look) followed by 6-second image presentation. The instruction presentation will remain constant within each experimental session. Images will be presented in random order from a bank of 300 images to minimize habituation. After each image offset, subjects will rate craving for cocaine using a 0-10 visual analog scale (0 = Not at All; 10 = Very Much) (Lopez et al., 2015). Craving, averaged across all trials in a session, will be the primary outcome. The manipulation will be repeated prior to each self-administration opportunity.

Progressive-Ratio Procedure. Following a 30-image trial, subjects will be offered the opportunity to earn the sampled cocaine dose on the Progressive-Ratio Procedure. We have a long history of using this procedure to assess the reinforcing effects of stimulant drugs ([name], 2008), including cocaine ([name] et al., 2010a; 2012a). It yields orderly, dose-related self-administration outcomes. Subjects will have a total of five opportunities to earn the dose they sampled at the outset of the session in order to provide multiple replication trials to determine the impact of the craving manipulation on drug self-administration (Ferster and Skinner, 1957; Spiga and Roache, 1997). The initial response requirement for a dose will be 400 mouse clicks. Response requirements will increase by 200 for each subsequent dose. For example, if a subject chooses cocaine at the first trial, earning that dose would require 400 responses. At the second opportunity, if he/she chooses to earn cocaine again, earning that dose would require 600 responses. If he or she elects not to earn cocaine at any given opportunity, the response requirement would not increase for the next opportunity. If a subject were to choose cocaine across all opportunities, the response requirements would be 400, 600, 800, 1000 and 1200 responses. The primary outcome is the number of cocaine doses earned.

Subjective-Effects and Physiological Measures. A subjective-effects questionnaire and physiological measures will also be used to assess cocaine effects and monitor safety.

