Subjective-Effects Measures. One subject-rated questionnaire that measure various aspects of mood and drug effect will be used: the Drug-Effect Questionnaire. This questionnaire is sensitive to stimulant drug effects ([name] et al., 2003).

Physiological Measures. Heart rate, blood pressure, heart rhythmicity and oral temperature will be recorded using a digital monitor. These outcomes are sensitive to stimulant drug effects ([name] et al., 2008; 2016).

Commodity Purchase Task (Appendix B). Commodity purchase tasks will be used to assess economic demand for chocolate, cigarettes, alcohol, and the cocaine sampling dose (Amlung et al., 2015; Bruner and Johnson, 2014; Murphy and MacKillop, 2006; [name] et al., ongoing). In these tasks, subjects are asked to indicate the hypothetical number of commodity units (i.e., 12 oz. sodas) they would purchase at a future date at monetary increments ranging from \$0.00 (free) to \$140/unit. In the cocaine task, participants will be asked to make choices based on the sampling dose they received earlier in the session. All choices are hypothetical and will not be purchased or administered. Subjects will complete the Commodity Purchase Tasks following approximately .25 h after the sampling dose.

Drug Dose and Administration. All drugs will be administered under double-blind conditions and under medical supervision. Doses of cocaine HCl will be prepared by weighing out the appropriate amount of powdered cocaine. The powder will then be mixed with lactose monohydrate powder, N.F. to make a total of 80 mg powder. Placebo will be prepared in an identical fashion, but will contain only lactose monohydrate powder. Doses of cocaine will be prepared individually for each subject. Doses of 0, 40 and 80 mg intranasal cocaine will be placed into individual glass vials labeled for each subject for each sampling session. The unit doses of cocaine proposed for the study have been administered to human subjects under similar controlled medical and laboratory conditions without adverse incident by the study team ([name] et al., 2008; 2010; 2016).

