Data Analysis. All data will be analyzed using SPSS (IBM Corporation, Armonk, NY). To test our primary hypothesis, self-reported craving scores and number of cocaine doses earned will be analyzed using two-factor repeated-measures General Linear Model (GLM) with data from the 30 subjects who complete the protocol. The α level will be set at $p \leq 0.05$. Data from subjects who do not complete will not be included in the analyses. Cocaine Dose (0, 40 and 80 mg) and Craving Manipulation (positive, negative and look) will be the factors of the ANOVA. A significant change in craving or self-administration will be inferred if the Interaction of Cocaine Dose and Craving Manipulation attains statistical significance. If the interaction attains statistical significance, the mean square error term will be used to conduct Tukey's HSD post-hoc test to make appropriate pair-wise comparisons. If baseline measures (e.g., craving) differ across conditions, they will be entered into the analysis as covariates. To test our secondary hypothesis, craving scores will be averaged for each of the nine conditions and compared with self-administration outcomes using Pearson correlations. Subjective-effect and physiological data following the sampling dose will be averaged across craving manipulation conditions because they will be collected prior to the craving manipulation and analyzed using cocaine dose and time as factors in a repeated-measures GLM. Exploratory analyses considering relevant biological variables (i.e., sex, age and race/ethnicity) will also be conducted.

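### The plan infers a change in craving from the dose-by-manipulation interaction and gives the manipulation effect itself no inferential role, so a reduction equal at all doses would be missed about 95% of the time

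*Combined protocol and SAP*

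**What the plan says.** The specific-aim paragraph of the Background states the hypothesis: "We hypothesize that focusing on the negative effects of cocaine use will decrease craving and reduce cocaine self-administration relative to the positive" and look conditions. It attaches no dose to the prediction.

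Section 7 labels two measures as primary. Under Regulation of Craving Manipulation: "Craving, averaged across all trials in a session, will be the primary outcome". Under Progressive-Ratio Procedure: "The primary outcome is the number of cocaine doses earned".

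The Data Analysis paragraph of Section 7 analyses each in a two-factor repeated-measures GLM (dose 0, 40, 80 mg; manipulation positive, negative, look) on the 30 completers, at alpha 0.05. Its inference rule is: "A significant change in craving or self-administration will be inferred if the Interaction of Cocaine Dose and Craving Manipulation attains statistical significance". Tukey comparisons follow only if that interaction is significant. The paragraph plans no test of the manipulation main effect and no negative-versus-look or negative-versus-positive contrast.

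Section 2 frames the objective around the drug: "The primary objective of this study is to determine the influence of a craving manipulation on the reinforcing effects of cocaine". Section 17 (Data Monitoring Plan) repeats that target.

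**The concern.** The hypothesis concerns the level of an outcome under one instruction compared with two others. The decision rule concerns whether that comparison changes with dose. These are different questions, and the data can answer yes to the first and no to the second.

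The gap matters most for craving. The same three instruction types and one image pool serve every session ("Images will be presented in random order from a bank of 300 images to minimize habituation"), so an effect of similar size at every dose is plausible. If that is what happens, the trial could show what the Background predicts, the stated rule would not infer it, and the two comparisons named in the hypothesis would never be opened. Turning to the main effect after a null interaction would then be a choice made with the data in view.

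**Working it through.** **Inputs from the documents.** 30 completers, 3 doses by 3 manipulations, each cell once per subject, alpha 0.05. The interaction is tested on F(4, 116) and the manipulation main effect on F(2, 58).

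**Inputs assumed.** The documents give no SD, effect size, power or dose pattern, so the sample size of 30 cannot be reproduced. The only available check is that the simulated null rejection rate of the interaction matches alpha (5.1%). Assumptions: residual SD 1; reduction d under negative focus; positive equal to look unless stated; subject-by-manipulation SD s of 0 or 0.5.

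**Step 1: an equal reduction cancels out of the interaction.** If the cell means are additive, mean(i, j) = a_i + b_j, each interaction term mean(i, j) − mean(i, ·) − mean(·, j) + mean(·, ·) is 0. For example, (negative − look at 80 mg) − (negative − look at 0 mg) = (−d) − (−d) = 0. The noncentrality is 0 for every d, so the rejection rate is alpha. Simulation gave 4.9-5.1% for d from 0.3 to 2.0. This requires sphericity or a correction; with strong heteroscedasticity by dose and no correction it was 7.2%, still only a false-positive rate.

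**Step 2: the main effect already in the model, d = 0.5 at every dose.** The deviations of the three manipulation means are −2d/3, d/3 and d/3, with sum of squares 2d²/3 = 0.1667. Noncentrality = 30 × 3 × 0.1667 / (1 + 3s²) = 15 / (1 + 3s²).
- s = 0: 15.0, power 93%.
- s = 0.5: 15 / 1.75 = 8.57, power 73%.

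**Step 3: the two contrasts in the hypothesis, averaged over dose.** SE = √[2(1/3 + s²)/30].
- s = 0: SE 0.149; d/SE = 0.5/0.149 = 3.35.
- s = 0.5: SE 0.197; d/SE = 0.5/0.197 = 2.54.

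The two contrasts share the negative condition, so their joint power was simulated: 83% and 54% for both significant in the predicted direction. Under the plan (interaction first, then Tukey showing negative below both others at the same dose) the figure is 2-3%.

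**Step 4: where the plan does as well or better.** Power to claim both comparisons; the planned range covers Tukey taken over 9 or 3 means:

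| Assumed pattern | As planned | Two dose-averaged contrasts |
|---|---|---|
| Equal, 0.5 at each dose; s = 0 to 0.5 | 2-3% | 54-83% |
| 80 mg only, 0.8; s = 0 to 0.5 | 28-51% | 12-25% |
| Graded 0/0.4/0.8, positive focus raising the outcome by half as much; s = 0.5 | 42-62% | about 47% |
| 80 mg only, 0.8, positive focus raising by half as much; s = 0.5 | 45-69% | about 19% |

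**Step 5: doses earned, with a floor.** The model is a 0-5 count with look means of about 2 at 40 mg and 3 at 80 mg, the same underlying reduction at every dose, and s = 0. As the placebo mean falls from 1.2 to 0.05 doses, the interaction is significant 8% rising to 74% of the time for a reduction of 0.8 dose, and 6% rising to 28% for 0.5 dose. At a placebo mean of 0.05, the planned claim succeeds 62-72% (0.8 dose) and 14-23% (0.5 dose) of the time. Both contrasts over 40 and 80 mg, here Holm-adjusted and so slightly understated, succeed 95-96% and 53-54%.

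**The case against.** **The rule says if, not only if, and the GLM contains the main effect.** This is correct: the plan does not forbid looking at it. But no other inference rule is written and the pairwise tests are gated, so the main effect has no prespecified standing. The complaint is about that missing role.

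**The 5% is a boundary case.** This stands. It applies to a shift that is constant on the observed scale. Craving is rated 0-10, after the sampled dose and, later in the session, after any doses earned, so the effect may vary with dose. With assumed look means of 1, 3 and 5 at the three doses and the same underlying reduction at each, a floor made the interaction significant about 16-17%, 44% and 81% of the time for reductions of 1, 1.5 and 2 points. With means of 4, 5 and 6 it stayed near 5%. A reader might infer that the plan misses any real craving effect 95% of the time; the documents do not support that.

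**For doses earned the interaction has a purpose.** This also stands. A reader might infer that the rule is equally wrong for both outcomes. But Sections 2 and 17 set the target as cocaine's reinforcing effects, the 0 mg condition is inert ("Placebo will be prepared in an identical fashion, but will contain only lactose monohydrate powder"), and of the procedure Section 7 says: "It yields orderly, dose-related self-administration outcomes". Specificity to active cocaine is a legitimate question there, and low placebo responding itself creates some interaction.

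**Averaging over dose is not always better.** True: the last three rows of the table show patterns where the plan equals or beats it. None of those patterns is the one hypothesised in the Background, which names no dose, but the cost is real.

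**This is a pilot study.** That excuses the absent power calculation. It does not reconcile the hypothesis with the test.

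**Conclusion.** For craving, the decision rule does not test the stated hypothesis and should be changed. An observed-scale reduction equal at all three doses is detected at about 5% whatever its size. That result needs no assumed SD or effect size, only sphericity or a correction for its absence. The comparison figures (73-93% for the main effect, 54-83% for both contrasts, at 0.5 SD) rest wholly on assumed inputs, as do the figures for patterns that favour the plan.

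For doses earned the finding is narrower. The interaction is defensible as a test of specificity to active cocaine, but as the sole route it can leave a reduction at 40 and 80 mg unclaimed.

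**What to change.** Reword the Data Analysis paragraph of Section 7:

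1. **Craving.** Test the primary hypothesis with the Craving Manipulation effect, followed by the negative-versus-look and negative-versus-positive contrasts averaged over the three doses. Claim the full hypothesis only if both contrasts are significant in the predicted direction; requiring both already controls the error of that joint claim, so no Holm adjustment is needed. Remove the interaction as a precondition.
2. **Doses earned.** Keep the interaction as a test of specificity to active cocaine, and add the same two contrasts over 40 and 80 mg, which match the objective in Section 2. Do not gate them on the interaction.
3. **Dose specificity of craving.** Retain the interaction, with within-dose Tukey comparisons, as a stated secondary test.
4. State how the conditional baseline covariates enter the contrasts.

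No new data, subjects or procedures are needed. The price is power for the primary craving claim when the effect is confined to 80 mg (assumed 0.8 SD: 12-25% against 28-51% as planned), and possibly no gain for dose-graded effects when positive focus also raises craving (about 47% against 42-62%). The secondary interaction test offsets this only in part.

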7. RESEARCH PROCEDURES

General Procedures. Subjects that meet the inclusion criteria will participate as outpatients at the University of Kentucky LHBP and Clinical Services Core (CSC). Subjects will be discharged at the end of each day, provided that they meet release criteria.

This experiment will require each subject to complete a total of one practice and nine experimental sessions over approximately two to three weeks. Experimental sessions will be conducted as outlined in the table below. We would like to note that the order of the experimental sessions (i.e., dose tested and craving manipulations) will be randomized across subjects. The practice session will familiarize subjects with the experimental routine and tasks, but no drug will be administered and subjects will receive instructions on each of the craving manipulation conditions (positive, negative, and look [neutral]).

Time	
0800	Arrival at LHBP. Drug and alcohol use restriction compliance verified. Transport to CSC.
0900	Baseline craving, subjective-effect and physiological measures completed.
1000	Subject samples intranasal dose available for that session. Subjective-effect and physiological measures completed at 15-minute intervals for 45 minutes. Commodity purchase tasks completed 15 minutes after sampling dose.
1045	Subject completes regulation of craving manipulation assigned for that session (positive, negative or look) and rates craving.
1050	Subject offered opportunity to work for dose on progressive-ratio schedule.
1100	Dose administered, if earned and physiological measures are within acceptable limits.
1115	Subjective-effects and physiological measures completed.
1130	Craving manipulation, craving measurement, progressive-ratio procedure and subjective-effects and physiological measures sequence completed. Repeats 4 more times at 45-minute intervals.
1530	Discharge from CSC. Return to LHBP for final sobriety testing, payment and release.
Note	Cocaine dose and craving manipulation will be presented in random order. A fully factorial design will be used so that all possible combinations are tested once each over nine sessions.

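### The pooled interaction error planned for Tukey's HSD is generally not the right error for comparing instructions within a dose; the standard error can be too small or too large, depending on dose

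*Combined protocol and SAP*

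**What the plan says.** Section 7, Data Analysis, fits a two-factor repeated-measures "General Linear Model (GLM) with data from the 30 subjects who complete the protocol", separately for craving and for doses earned. "Cocaine Dose (0, 40 and 80 mg) and Craving Manipulation (positive, negative and look) will be the factors of the ANOVA". The note under the session table in the same section adds: "A fully factorial design will be used so that all possible combinations are tested once each over nine sessions".

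The inferential rule is: "A significant change in craving or self-administration will be inferred if the Interaction of Cocaine Dose and Craving Manipulation attains statistical significance". For the follow-up: "If the interaction attains statistical significance, the mean square error term will be used to conduct" Tukey's HSD on whatever pairs are appropriate. The plan does not say which of the three within-subject error terms is meant or which pairs will be compared. It names no sphericity correction and no contrast-specific error.

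The Background section gives the comparisons of interest: the negative instruction is expected to "decrease craving and reduce cocaine self-administration relative to the positive and “look” conditions". Doses earned is bounded at 0 and 5: "Subjects will have a total of five opportunities to earn the dose they sampled at the outset of the session".

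**The concern.** A significant interaction shows only that the instruction effect differs by dose. It does not show that the negative instruction lowers craving or self-administration, or at which dose. The pairwise tests have to show that, so their standard errors matter.

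A comparison of two instructions at one dose contains two sources of within-subject noise: how differently people respond to the instructions overall (subject-by-manipulation variation), and how that response varies by dose within a person (the interaction residual). The interaction error holds only the second. It also averages over doses, so it fits each dose only if the differences are equally variable at 0, 40 and 80 mg. A count limited to 0–5 may well not satisfy that when placebo is one of the levels.

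**Working it through.** **No figure to reproduce.** The documents give no power, effect size, SD, correlation or expected mean by dose for either outcome. Every ratio below rests on an algebraic identity or on assumed variances.

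**Inputs from the plan.** n = 30 completers; 3 doses × 3 manipulations = 9 cells, one session each; "The α level will be set at" 0.05. With one session per cell, the interaction error is MS(dose × manipulation × subject), written MS_DMS, with 2 × 2 × 29 = 116 df.

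**Step 1: what the planned SE is.** SE used = sqrt(2 × MS_DMS / n).

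**Step 2: what it should be when variances are equal across doses.** Let σ²_ms be the subject-by-manipulation variance and σ² the residual.
- E[MS_DMS] = σ² and E[MS_MS] = σ² + 3σ²_ms, where MS_MS is the manipulation × subject mean square.
- The variance of a within-dose difference is 2(σ² + σ²_ms) = 2(MS_MS + 2 MS_DMS)/3.
- With R = MS_MS / MS_DMS, SE used / SE true = sqrt(3/(R + 2)).

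| R | σ²_ms / σ² = (R − 1)/3 | SE used / true |
|---|---|---|
| 1 | 0 | 1.00 |
| 2 | 1/3 | sqrt(3/4) = 0.87 |
| 4 | 1 | sqrt(3/6) = 0.71 |

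The ratio is the same at every dose, including 0 mg. The planned SE is right only if R = 1, that is, if subjects do not differ in how they respond to the instructions.

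**Step 3: unequal variances.** Suppose the residual SD at 0 mg is half that at 40 and 80 mg, with no subject-by-manipulation variance. The pooled error is (0.25 + 1 + 1)/3 = 0.75. The ratio is sqrt(0.75/0.25) = 1.73 at 0 mg and sqrt(0.75/1) = 0.87 at the active doses.

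**Step 4: simulated 0–5 counts, n = 30, means assumed.** All rows include some subject-by-manipulation variation, except that the first row spans a range of assumed SDs.

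| Assumed pattern (0 / 40 / 80 mg) | SE used / true (0 / 40 / 80 mg) |
|---|---|
| Strong floor, no ceiling (means about 0.5 / 2.2 / 3.2) | 1.20–1.47 / 0.74–0.90 at both active doses |
| Means about 0.8 / 2.5 / 3.3 | 1.12 / 0.82 / 0.87 |
| Weaker floor (0 mg mean about 1.3) | 1.02 / 0.91 / 0.92 |
| Near ceiling at 80 mg (about 1.4 / 2.5 / 4.4) | 0.89 / 0.79 / 1.23 |
| Means about 1.7 / 2.5 / 3.3, R about 4 | 0.72 / 0.68 / 0.72 |

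The direction at a given dose therefore depends on means and variances that the documents do not give.

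**Step 5: effect on the error rate.** It depends on which means Tukey covers.
- Nine means: q(0.95; 9, 116) = 4.47, so |t| > 4.47/√2 = 3.16, a nominal 0.2% per pair. At R = 4 this is a cut-off of 3.16 × 0.71 = 2.24 on the true-SE scale, and the simulated error per pair is about 2–3%.
- Three instructions within a dose: |t| > 2.37. At R = 2 the effective cut-off is 2.37 × 0.87 = 2.06, about that of an unadjusted two-sided 5% test on 29 df (2.05). At R = 4 it is 2.37 × 0.71 = 1.68.

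These rates ignore the requirement of a significant interaction.

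**The case against.** **The direction is not established.** A reader might infer that the SE is simply too large at 0 mg and too small at 40 and 80 mg. That needs a strong placebo floor and no ceiling at 80 mg. Section 7 says only that the procedure gives dose-related outcomes. Step 4 shows the pattern nearly vanishing with a weaker floor and reversing near a ceiling. This objection stands in full. It stands more strongly for craving, which is rated 0–10 after cocaine images at every dose, so the documents give no reason to expect a floor at 0 mg.

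**The false-positive rate is not shown to be gross.** With Tukey over nine means, simulated false declarations of negative versus look at 40 or 80 mg were roughly 1–4% without the interaction gate. With the gate, under a global null, they were 0.6–1.4%. Both are below 5%. This stands for the nine-mean reading. Two limits apply: the gate gives no protection to a null contrast once a real effect elsewhere opens it, and under the three-mean reading the margin is gone by about R = 2.

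**The penalty for 36 pairs is inferred.** The plan does not say that all pairs among nine means will be compared. This stands.

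**A power gain is not a consequence of correcting the SE.** For a true reduction of about 1 dose at 80 mg, ungated simulated power was 59% with nine-mean Tukey and 70% with Holm over four paired contrasts. That gain comes from testing fewer pairs; the correct SE at 80 mg in that setting is larger, which lowers power. With an effect at 80 mg only, the comparison is about 57% versus 63%. Tukey over three means gave about 82%, with a higher ungated error rate. This stands.

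**The error term is not named.** Reading it as the interaction error is an inference, but it follows directly from the sentence, which ties the term to a significant interaction.

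**Conclusion.** The point holds in a limited form. A single pooled interaction error is in general not the right error for the hypothesised comparisons within a dose, and the plan has no safeguard against this. Under equal variances the SE is too small at every dose whenever R exceeds 1: by 13% at R = 2 and 29% at R = 4. This part applies to both craving and doses earned.

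For doses earned, unequal variance by dose adds a second error of uncertain direction. The figures of 20–47% too large at 0 mg and 10–26% too small at 40 and 80 mg are conditional on a strong placebo floor and no ceiling at 80 mg. The planned SE is correct if R = 1 and variances are equal; the documents offer nothing to show that either condition holds. The documents support neither a fixed direction by dose, nor a claim of gross type I error inflation, nor a promised power gain.

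The conclusion rests on reading the unnamed term as the interaction error. The consequence is pairwise conclusions that may be miscalibrated by dose. It does not affect the interaction test itself.

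**What to change.** For both outcomes, replace the pooled-error Tukey step with four pre-specified contrasts: negative versus look and negative versus positive, at 40 mg and at 80 mg. Compute each from within-subject paired differences, with its own SE on 29 df. State the multiplicity adjustment, for example Holm over the four within each outcome (first-step cut-off |t| > 2.66). These SEs do not depend on R or on equal variances across doses.

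If Tukey's HSD is kept, the plan should at least name the error term and list the pairs it will cover.

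The change is to analysis wording only and needs no new data. The cost is 29 rather than 116 error df per contrast, and no adjusted test of pairs outside the hypothesis. Any gain or loss of power depends on which pairs Tukey would have covered and on the doses at which an effect exists, so it should not be offered as the reason for the change.

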Appendix A

Subject-Rated Drug-Effect Questionnaire Description

Drug Effect-Questionnaire (DEQ)-VAS

Individual questions are presented sequentially, one at a time. Subjects rate their response to each question by marking a 100-unit line anchored with "Not at All" on the left side and "Extremely" on the right side.

(1) Is the drug producing "**ANY EFFECT**" right now? (2) Is the drug producing any "**BAD EFFECTS**" right now? (3) Is the drug producing any "**GOOD EFFECTS**" right now? (4) Is the drug making you feel "**HIGH**" right now? (5) Are you experiencing a "**RUSH**" from the drug right now"? (6) How much do you "**LIKE**" the drug right now? (7) Is the drug making you feel "**STIMULATED**" right now? (8) Is the drug "**IMPAIRING YOUR PERFORMANCE**" right now? (9) Is the drug "**IMPROVING YOUR PERFORMANCE**" right now? (10) Based on how the drug effect feels right now, would you be willing to "**TAKE THIS DRUG AGAIN**"? (11) Based on how the drug effect feels right now, would you be willing to "**PAY FOR THIS DRUG**"? (12) Is the drug making you feel "**ACTIVE, ALERT OR ENERGETIC**" right now? (13) Is the drug making you feel "**EUPHORIC**" right now? (14) Is the drug making you experience an "**IRREGULAR OR RACING HEARTBEAT**" right now? (15) Is the drug making you "**TALKATIVE OR FRIENDLY**" right now? (16) Is the drug making you feel "**NAUSEATED, QUEAZY OR SICK TO YOUR STOMACH**" right now? (17) Is the drug making you feel "**SHAKY OR JITTERY**" right now? (18) Is the drug making you feel "**NERVOUS OR ANXIOUS**" right now? (19) Is the drug making you feel "**RESTLESS**" right now? (20) Is the drug making you feel "**SLUGGISH, FATIGUED OR LAZY**" right now?

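### Baseline covariates enter the primary model only if they differ across conditions, which is a near-chance trigger and the wrong reason to adjust

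*Combined protocol and SAP*

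**What the plan says.** The primary analysis (section 7, Data Analysis) is a two-factor repeated-measures GLM of craving and of doses earned in 30 completers. The factors are dose (0, 40, 80 mg) and craving manipulation (positive, negative, look). Inference rests on one term: "A significant change in craving or self-administration will be inferred if the Interaction of Cocaine Dose and Craving Manipulation attains statistical significance".

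Covariates are handled in one sentence: "If baseline measures (e.g., craving) differ across conditions, they will be entered into the analysis as covariates". Craving is only an example. The sentence gives no test, no cut-off for a difference, no closed list of measures and no form for the covariate.

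The section 7 session table puts the baselines at 0900 ("Baseline craving, subjective-effect and physiological measures completed"), the sampling dose at 1000 and the first manipulation at 1045. Its note adds: "Cocaine dose and craving manipulation will be presented in random order". The scale of the 0900 craving rating is not described. The only craving scale described is the one used with the cue images ("After each image offset, subjects will rate craving for cocaine using a 0-10 visual analog scale"), and none of the 20 questionnaire items in Appendix A asks about craving.

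**The concern.** Adjusting for a baseline in a randomised crossover is worthwhile when a session's baseline predicts that session's outcome, because residual variance then falls. Whether the baseline means happen to differ across the nine conditions is a separate matter. With random order and baselines taken before dosing, such differences are expected to arise by chance. The rule therefore lets chance choose the primary model, and in most trials it discards a covariate that has already been collected.

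What is at stake is precision for the interaction test with 30 subjects, and a primary model that is not fixed in advance. There is also a gap in form. Baseline is measured in every session, whereas the usual covariate in a repeated-measures GLM is one value per subject.

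**Working it through.** **Inputs from the documents.** 30 completers; 3 x 3 within-subject conditions, each tested once; alpha 0.05 (section 7, Data Analysis; repeated in section 17); random order; baselines at 0900. The documents give no power, effect size, SD or baseline-outcome correlation, so there is no stated figure to reproduce.

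**Assumptions.** Negative instruction lowers craving by 0.8 session-level (residual) SD at 40 and 80 mg only. Errors are normal and spherical. The within-subject baseline-outcome correlation r runs from 0.1 to 0.7. Baseline tests, if made, are at 5%.

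**1. How often the rule fires (craving only).** One test, either of the interaction or across all nine conditions: 5%. Three tests (dose, manipulation, interaction): 1 - 0.95^3 = 14.3%. The covariate is thus left out in about 86-95% of trials.

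**2. Unadjusted power.** The dose pattern (0, 1, 1) has centred sum of squares 2 - 4/3 = 2/3. The instruction pattern (1, 0, 0) has 1 - 1/3 = 2/3. The noncentrality is 30 x 0.8^2 x (2/3) x (2/3) = 8.53. Error df are 2 x 2 x 29 = 116. Power of F(4,116) is 62%.

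**3. Always adjusting for the session's own baseline.** Noncentrality becomes 8.53/(1 - r^2) and one error df is lost, giving F(4,115). The equivalent number of unadjusted subjects is 30/(1 - r^2).

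| r | Noncentrality | Power | Equivalent subjects |
|---|---|---|---|
| 0.1 | 8.62 | 62% | 30 |
| 0.2 | 8.89 | 64% | 31 |
| 0.3 | 9.38 | 66% | 33 |
| 0.5 | 11.38 | 76% | 40 |
| 0.7 | 16.73 | 91% | 59 |

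**4. The conditional rule.** In simulation, adjusting only when an omnibus or factor-level baseline test fires gives 61-66% power over r = 0.2 to 0.7. That recovers little of the gain in step 3.

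**5. Type I error (null simulation).** Unadjusted, always-adjusted and fixed-rule analyses all lie at 3.5-5.4%. If the analyst may take either result in any trial, the rate is 5.9, 6.7, 7.3 and 8.4% at r = 0.2, 0.3, 0.5 and 0.7. If that choice is open only in triggered trials, it is about 5-6%.

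**6. Doses earned.** An illustrative 0-5 count was simulated from a latent normal scale. Latent r of 0.2, 0.3, 0.5 and 0.7 shrinks to 0.15, 0.23, 0.38 and 0.53. Power moves from 41 to 41%, 41 to 43%, 40 to 46% and 40 to 54%.

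**7. Form of the covariate.** Interaction contrast coefficients sum to zero over a subject's nine sessions. A value that is constant over those sessions contributes nothing to the contrast of the baseline, so a subject-level covariate cannot remove a session-level difference, which is the very thing that triggers the rule.

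**The case against.** **The trigger is nearly fixed already.** Data Analysis sets alpha at 0.05 and names the factors in the same paragraph, so the natural reading is the same GLM run on the baseline. This stands, and it is why 5-14% is used here. Tukey's HSD, the only pairwise method named, would fire about 5% of the time on nine baseline means. A reader might infer a rule that fires in most trials: 59-60% with 36 unadjusted pairwise tests, or 72-98% with 25 independent measures. The documents do not support this. They name no unadjusted pairwise tests, and nearly all 20 questionnaire items ask about a drug effect before any dose has been given that session, so floor-level answers are likely.

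**The text instructs.** Measures that differ are to be entered; no choice of result is offered. This also stands, and it confines the 6-8% error rate to an upper bound.

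**The gain rests on an unknown r.** True. Nothing shows that one 0900 rating predicts a session mean of up to 150 later ratings (30 images x 5 opportunities) with r of 0.3 or more, and this is a self-described pilot.

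**Imbalance is not purely chance.** Each combination occurs once, so a non-first 80 mg session follows another 80 mg session with probability 2/8, against 3/8 for a session at another dose. Carry-over could therefore shift baselines slightly, and so could restricting the analysis to completers. Neither makes an observed difference the right criterion.

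**The adjusted univariate test has no sphericity correction.** With assumed session SD ratios by dose of 1/3:2/3:1 and 0.1:0.5:1, F(4,115) has Type I error of about 6.2-7.6%. The planned F(4,116) without correction is no better, at 6.5-7.8%. A Greenhouse-Geisser epsilon computed from the adjusted residuals restores 4.4-4.7%. The objection therefore adds to the fix without defeating it.

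**Conclusion.** The concern holds as a matter of model choice and precision. The condition tests the wrong thing, fires in about 5-14% of trials on the ordinary reading, and so forgoes whatever the 0900 rating offers in most trials. Under the assumed effect the loss is about 2 points of power at r = 0.2, 5 at 0.3, 14 at 0.5 and 30 at 0.7 (64, 66, 76 and 91% against 62%, from unrounded values). It is smaller for doses earned. These figures assume sphericity and no corrected test, and r is unknown; below 0.3 there is little to gain.

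A reader might infer that the rule inflates the false-positive rate. It does not. The unadjusted analysis is valid, and a fixed conditional rule stays at or below nominal within simulation error. About 6-8% would require freedom to take either result in any trial, which the sentence does not grant. Nor do the documents specify a damaging covariate form, such as an uncentred one; they leave the form open. The change is worth making because it is cheap and fixes the primary model in advance.

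**What to change.** Before the data are unblinded:

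- Delete the condition on baseline differences.
- Name the 0900 craving item and its scale, for example the 0-10 scale given before any image.
- State that each session's own 0900 rating enters the craving and doses-earned analyses as a session-level covariate whatever the observed differences, and that no other baseline measure is added because of a baseline test.
- Test Dose x Manipulation in its own stratum, against the Subject x Dose x Manipulation error less one df, F(4,115), with a Greenhouse-Geisser correction computed from the adjusted residuals. In SPSS the adjusted model is a univariate GLM on the 30 x 9 = 270 session records, with Subject, Dose, Manipulation and their two-way interactions plus the covariate. The epsilon is a separate step.
- Alternatively, use a mixed model with random subject, subject-by-dose and subject-by-manipulation effects, variances allowed to differ by dose, and Kenward-Roger or Satterthwaite df.
- Base post-hoc comparisons on the adjusted means.
- Report the unadjusted repeated-measures GLM, with Greenhouse-Geisser correction, as a sensitivity analysis.

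The cost is one error df (116 to 115), a little more analysis work and an assumed common slope across doses, which is least secure for doses earned if these sit near zero at 0 mg. No new data are needed if the 0900 rating is already on a fixed scale. If it is not, or if the sponsor expects r below 0.3, prespecifying no adjustment would also remove the data-dependent choice.
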